Study protocol 2021-04-26

Investigating the anabolic response to resistance exercise during and after critical illness.

Study acronym

ARTIST 1 & 2

Primary investigator

[name] PhD

Version history

2022-02-15: Amendment to ethical review authority regarding screening and recruitment of patients in Study 2.

2022-03-10: Minor amendment regarding dose of oral protein and labeled phenylalanine in Study 2.

2022-07-10: Amendment to ethical review authority regarding exclusion criteria for therapeutic anticoagulation in Study 2.

2023-01-17: Minor amendment regarding exclusion criteria # 13 and 14 in Study 2.

2023-05-08: Amendment to ethical review authority regarding additional data collection (SF-36 and hand grip strength).

2023-10-23: Minor amendment regarding sample size target in Study 2.

Aim

The overall aim of this project is to determine the anabolic response to resistance exercise during and after critical illness.

Hypothesis

1) Resistance exercise, in addition to amino acid supplementation and routine physiotherapy, results in an improved muscle protein balance in ICU patients compared to amino acid supplementation and routine physiotherapy alone.

2) Patients recovering from critical illness have an impaired anabolic response to resistance exercise 3-6 months after ICU stay as compared to healthy controls.

Overview of the field

The debilitating impact of critical illness has been recognized for several decades. Disability related to intensive care is now described as a syndrome called ICU-acquired weakness (ICUAW). ICUAW affects up to 70% of ICU patients and is most common with higher illness severity. The pathophysiology is heterogenous, and involves muscle protein breakdown, altered bioenergetics, axonal injury and impaired excitation-contraction coupling. Patients that develop ICUAW require longer hospitalization and have a higher risk of death [1].

Weakness also has significant long-term consequences. In a landmark study, Herridge et al observed that predominantly young and previously healthy survivors of acute respiratory failure had reduced exercise capacity up to five years after ICU stay [2]. Physical function was unrelated to residual pulmonary dysfunction. Long-term disability was associated with significant health care costs, delayed return to work, and overall poor quality of life.

Preventing muscle atrophy is a potential way to counteract weakness. Critical illness is associated with a rapid loss of skeletal muscle, which may exceed 10% of lean body mass in the first week of intensive care [3,4]. Dos Santos et al found that a majority of ICU survivors had not recovered their muscle volume up to six months after hospital discharge [5].

During critical illness there is a dramatic increase in muscle protein breakdown, while synthesis is unaltered [6]. The result is a net loss of total body protein. Aging and comorbid conditions also contribute toward a resistance to anabolic signals, which may be exacerbated by immobilization and systemic inflammation [7]. Our research group has previously found that nutritional interventions such as amino acid supplementation can improve whole-body protein balance in ICU patients [8,9], but the effect on muscle metabolism is still unknown. Studies in exercise physiology have demonstrated that resistance training and amino acid ingestion have synergistic effects on muscle protein synthesis in healthy subjects [10]. It is therefore an appealing therapy to counteract muscle wasting in ICU, and to regain muscle mass during convalescence.

Despite several clinical trials, there remains equipoise regarding the efficacy of exercise in improving physical function in-ICU or after discharge [11,12]. These mixed signals are unsurprising given the heterogeneous causes of ICUAW. Only a few studies in this field assess

muscle architecture or cellular signaling in response to training [13,14]. However, the gold standard in determining the anabolic response to exercise is to directly measure the effect on protein synthesis and breakdown. To our knowledge there is still no published research using this methodology in critically ill patients.

Project description

The project consists of two studies. Study 1 will be conducted in the ICU. Study 2 will recruit study subjects who have been discharged from hospital after ICU stay.

Study populations:

Study 1 will recruit adult ICU patients suitable for active mobilization, which is already standard care in the unit at Karolinska University Hospital Huddinge.

Inclusion criteria:

1. Adult (≥ 18 years) ICU patient.
2. Suitable for active mobilization as determined by the attending physician and physiotherapist.
3. Not expected to be discharged or transferred from the unit within 24 h.
4. Functioning arterial line in situ.

Exclusion criteria:

1. Not able to provide informed consent.
2. Systemic anticoagulation with LMWH/UFH/DOAC in therapeutic dose range for deep vein thrombosis or pulmonary embolism, or dual antiplatelet therapy. If LMWH is administered twice daily, the patient is eligible for participation provided that vascular access is performed at nadir prior to the first daily dose.
3. Clinically significant inherited or acquired disorder of hemostasis.
4. Morbid obesity that interferes with femoral cannulation or doppler measurements.
5. Hemodynamic instability requiring ongoing volume resuscitation with crystalloid solutions or blood products.
6. Lower-limb amputee.
7. Lower-limb arteriosclerotic disease with critical ischemia.
8. Metastatic cancer or active hematological malignancy.
9. Inherited disorder of amino acid metabolism.
10. Chronic muscle, neuromuscular och neurologic disease with prior documentation of clinically significant lower-limb involvement.

11. Pregnancy.
12. Single organ failure not requiring invasive mechanical ventilation prior to enrollment.

Study 2 will include patients 3-6 months after hospital discharge. All patients treated for ≥ 3 days in an ICU at Karolinska University Hospital will be screened for eligibility.

Inclusion criteria:

1. Adult (≥ 18 years) subject previously admitted to an ICU at Karolinska University Hospital for ≥ 3 days and discharged from hospital (intervention group).

OR

2. Adult (≥ 18 years) subject without a history of ICU admission (control group).

Exclusion criteria (applies to both intervention and control group):

1. Not able to provide informed consent.
2. >6 months since ICU discharge.
3. Systemic anticoagulation with warfarin or dual antiplatelet therapy.
4. Clinically significant inherited or acquired disorder of hemostasis.
5. Lower-limb amputee.
6. Lower-limb arteriosclerotic disease with critical ischemia.
7. Recent fracture in lower limbs or significant osteoarthritis limiting movement in knee or hip joint.
8. Metastatic cancer or active hematological malignancy.
9. Inherited disorder of amino acid metabolism.
10. Chronic muscle, neuromuscular och neurologic disease with prior documentation of clinically significant lower-limb involvement.
11. Pregnancy.
12. Single organ failure not requiring invasive mechanical ventilation during ICU stay.
13. Intubated only for airway protection with no other organ failure(s) during ICU stay.
14. Planned postoperative care in ICU after elective cardiothoracic surgery.

Intervention and controls:

- Study 1: All patients will perform a physiotherapist-led session of standardized active mobilization. An intravenous infusion of mixed amino acids is administered concurrently.

Patients randomized to the intervention group will perform weighted resistance exercise with the leg catheterized for blood sampling as a part of their physiotherapy session.

- Study 2: All subjects will perform standardized lower extremity resistance exercise in conjunction with enteral protein supplementation. An age- and sex-matched group of healthy controls will be used for comparison.

Outcomes:

- Study 1: The primary outcome is the difference in change between the intervention and control groups in lower limb protein balance, from baseline to post-intervention. Other parameters of muscle protein kinetics (protein breakdown and synthesis) will be reported as secondary outcome measures.
- Study 2: The primary outcome is the difference between patients and healthy controls in fractional rate of muscle protein synthesis, from baseline to post-intervention. The impact of exercise on anabolic/catabolic signaling pathways in muscle fibres will be reported as secondary outcome measures. Planned post-hoc analyses include characterization of metabolomics and hormonal profiles in responders and non-responders.

Study protocols

Study 1

At the beginning of the protocol, a primed intravenous infusion of labeled ring-²H₅-phenylalanine (bolus 2.94 µmol/kg, infusion rate 2.94 µmol/kg/h) and ²H₃-methylhistidine (bolus 0.06 µmol/kg, infusion rate 0.06 µmol/kg/h) is started to achieve a steady state of tracer dilution in arterial blood and continued until the end of the protocol. A femoral venous catheter is then sited under local anaesthesia for lower limb blood sampling, with the tip placed just above the junction of the greater saphenous vein and common femoral vein. The physician placing the catheter is free to determine the side of placement depending on the vascular anatomy on ultrasound investigation. A standardized measurement of upper and lower limb muscle thickness is also performed to quantify the baseline muscle mass of study subjects [15].

After 165 minutes of tracer infusion, four 2 ml samples from arterial and lower limb venous blood and femoral artery blood flow measurements on the side of the catheterized leg are performed at five minute intervals. Doppler blood flow measurements will be performed using a high-frequency linear probe with a fixed probe angulation at a level immediately cranial to the

branching of the deep femoral artery. The end-diastolic inner diameter of the vessel is determined at the same level. Immediately after the baseline measurements, an intravenous infusion of mixed amino acids (Glavamin, Fresenius Kabi) is administered at a maximum rate of 0.1 g/kg/h.

The study subjects will then participate in a physiotherapy session of protocolized active mobilization. While sitting on the side of the bed, patients in the intervention group will be encouraged to perform weighted leg extensions with the leg catheterized for blood sampling, targeting 8-12 repetitions to failure in three sets. The physiotherapist in charge will document the number of repetitions and other items of the mobilization protocol performed.

After returning to a supine or semi-recumbent position, new blood samples and blood flow measurements as described above are performed to determine the change in lower limb protein balance every 30 minutes up to 90 minutes post-intervention. At the completion of the protocol the infusions of labeled and unlabeled amino acids are stopped and the femoral vein catheter is removed. The protocol is illustrated in [Figure 1](#).

[figure not shown]

Figure 1. A schematic illustration of the protocol in [Study 1](#) (not to scale).

All other aspects of treatment will be determined by the attending physician and care team, with a request that the rate of enteral and parenteral nutrition remains unchanged from 06:00 in the morning until the end of the protocol.

Study 2

Study subjects will arrive at the study site in the morning in a fasted state. After a baseline physical examination, a peripheral venous catheter and an arterial line are placed in an upper extremity under local anaesthesia. A primed intravenous infusion of ring-²H₅-phenylalanine (bolus 2.94 μ mol/kg, infusion rate 2.94 μ mol/kg/h) is started to achieve steady state distribution of tracer between plasma and the intracellular precursor pool, and continued until the end of the protocol. During the infusion period a standardized ultrasound measurement of lower limb muscle thickness and grip strength is performed to quantify the baseline muscle mass and function of study subjects. Charlson Comorbidity Index, Clinical Frailty Scale and RAND 36-item Short Form Health Survey are reported through self-assessment. After 150 minutes of tracer infusion, a baseline muscle biopsy of ~150 mg is extracted from the non-dominant vastus lateralis muscle under local anaesthesia. Blood samples are drawn at baseline (plasma amino acids and lipid profile, inflammatory markers, white blood cell count, hormonal profile and metabolomics) and at 15 minute intervals during the infusion period to determine tracer enrichment.

Subjects will then perform a short program of standardized quadriceps resistance exercise with the dominant leg, consisting of leg extensions in a flywheel inertia training machine targeting ten repetitions in four sets. Afterwards the subject will ingest a commercially available protein supplement containing 24 g of hydrolyzed whey protein over 5 minutes. To avoid diluting the ratio of labeled/unlabeled phenylalanine, 235 μ mol of ring-²H₅-phenylalanine is added to the beverage. A second biopsy is extracted from the contralateral vastus lateralis muscle used in the training session 150 minutes from the start of protein intake. The protocol is illustrated in [Figure 2.](#)

[figure not shown]

Figure 2. A schematic illustration of the protocol in Study 2 (not to scale).

Calculations

Study 1

Lower limb protein balance will be determined using a two-pool model [6]. Net balance (NB) of phenylalanine is derived using the Fick principle:

$$NB = (C_A - C_V) * PF$$

where C_A = arterial content (nmol/ml); C_V = venous content (nmol/ml); and PF = plasma flow (ml/min).

The rate of appearance (Ra) approximates protein breakdown and is calculated as:

$$Ra = C_V * [1 - (E_V/E_A)] * PF$$

Where E_A and E_V are the arterial and venous enrichments of tracer expressed as molar percentage excess and calculated as an average of the four blood samples in each measurement series.

The rate of disappearance (Rd) approximates protein synthesis and is calculated as:

$$Rd = NB + Ra$$

Study 2

Fractional synthesis rate (FSR) of muscle protein is calculated as

$$FSR = (E_B(t_2) - E_B(t_1)) / \int_{t_1}^{t_2} E_P(t) dt$$

Where E_B is the enrichment of bound amino acid, E_P enrichment of the precursor pool, t_1 and t_2 the duration of tracer infusion at the time of the first and second biopsy respectively.

Statistical considerations

Randomization

In Study 1, randomization will be determined using a computer-generated sequence in permuted blocks of four. Treatment allocation is concealed in opaque envelopes prepared by a research associate not involved in the study. The envelope is opened by the physiotherapist supervising the exercise session just before the intervention. Research staff in charge of outcome assessment are blinded to allocation until all data analysis is complete.

Sample size

As variation in muscle protein balance between ICU patients is very large [16], only paired comparisons will allow for studies of small-moderate size to find an effect. Unfortunately, there is no published data that describes the variation in repeated measures of muscle protein balance in ICU patients to support a formal power calculation. For Study 1, the best available estimate of effect size comes from pooled results on changes in whole-body protein balance during nutritional interventions. Using this data, we determine that 10 patients in each treatment arm are required to observe a mean change from negative to neutral lower limb muscle protein balance. To account for potential dropouts we will enroll a total of 24 patients.

For Study 2, there is no data from similar studies in this population on which to accurately estimate a treatment effect for sample size calculation. A target of 20 post-ICU patients and 20 matched controls has been chosen to allow for potential characterization of responders and non-responders in the post-intensive care group.

Statistics

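### Do the two discharge dates in Study 2's eligibility rules, and a 3-month minimum that no numbered criterion carries, leave the patient group undefined?

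*Protocol*

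**What the plan says.** Four places in the protocol bear on when a Study 2 patient may be studied.

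- **Study populations, Study 2, opening sentence:** "Study 2 will include patients 3-6 months after hospital discharge". It gives a lower and an upper bound, both counted from hospital discharge.
- **Study 2 inclusion criterion 1:** an adult "subject previously admitted to an ICU at Karolinska University Hospital for ≥ 3 days and discharged from hospital (intervention group". The patient must have left hospital, but no interval is given.
- **Study 2 exclusion criterion 2:** ">6 months since ICU discharge". This is an upper bound only, counted from ICU discharge.
- **Hypothesis 2:** an "impaired anabolic response to resistance exercise 3-6 months after ICU stay as compared to healthy controls". It gives both bounds, counted from the ICU stay.

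The Project description adds only that "Study 2 will recruit study subjects who have been discharged from hospital after ICU stay", with no interval. The exclusion list is headed "Exclusion criteria (applies to both intervention and control group", but criterion 2 cannot bite on controls, who by inclusion criterion 2 have never been in an ICU.

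**The concern.** Time since illness is part of the hypothesis, so the rules that fix it deserve a close reading. Two things look wrong.

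First, the 3-month minimum stands in the opening sentence but in no numbered criterion. Someone screening from the numbered list alone could accept a patient who went home two weeks ago, well before the recovery stage that the hypothesis describes.

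Second, the upper limit is stated twice, from two different dates, and nothing says which prevails. A patient can satisfy one and fail the other. If both apply, a long hospital stay after ICU uses up part of the eligible period. The Overview of the field says "Patients that develop ICUAW require longer hospitalization and have a higher risk of death". If some of that longer stay falls after the ICU, the patients of most interest would have the least time in which they could be studied.

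At stake would be a group of 20 patients at mixed or unintended stages of recovery, compared with 20 controls, and a responder analysis that is harder to interpret.

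**Working it through.** There is no trial figure to reproduce. The check is whether the stated limits can hold together, and what they then select.

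**Inputs.** From the protocol: 3 to 6 months after hospital discharge (opening sentence), not more than 6 months after ICU discharge (exclusion 2), and 3 to 6 months after ICU stay (hypothesis 2). Assumed: H, the months in hospital between ICU discharge and hospital discharge. The protocol gives no value or distribution for H; all that is certain is that H is at least 0.

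**Step 1: one time scale.** Count everything in months since ICU discharge.

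- Opening sentence: from H + 3 to H + 6.
- Exclusion 2: up to 6.
- Both together: from H + 3 to 6, a period of length max(0, 3 − H).

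**Step 2: compare with hypothesis 2.** Because H ≥ 0, the start H + 3 is never below 3, and the end is 6. Every patient admitted under both rules is therefore within 3 to 6 months of ICU discharge. This holds whatever H is.

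**Step 3: length of the eligible period for assumed H.**

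| H (months) | Eligible period since ICU discharge | Length (months) |
|---|---|---|
| 0 | 3 to 6 | 3 |
| 0.25 | 3.25 to 6 | 2.75 |
| 0.5 | 3.5 to 6 | 2.5 |
| 1 | 4 to 6 | 2 |
| 2 | 5 to 6 | 1 |
| 3 | 6 only | 0 |

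These are lengths of calendar time, not shares of patients. A patient with H above 3 could not be enrolled.

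**Step 4: patients on whom the passages appear to disagree.**

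- H = 0.5, studied 1 month after ICU discharge, so 1 − 0.5 = 0.5 month after going home. This patient passes inclusion 1 and exclusion 2 but fails the opening sentence: not eligible.
- H = 1.5, studied 5 months after hospital discharge, so 5 + 1.5 = 6.5 months after ICU discharge. This patient meets the opening sentence but fails exclusion 2: not eligible.
- H = 1, studied 2.5 months after hospital discharge, so 2.5 + 1 = 3.5 months after ICU discharge. This patient fits hypothesis 2 and exclusion 2 but fails the opening sentence: not eligible.

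Each case has a definite answer once all the rules are applied. The first goes wrong only if the opening sentence is ignored.

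**Step 5: would a single date be better?** Counting only from ICU discharge would admit the third patient, who has been home for less than 3 months. Counting only from hospital discharge would admit the second, who is more than 6 months past the ICU. The combined rule keeps both out.

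**The case for a change.** The best case for a change is that eligibility should not have to be assembled from two places. The numbered list repeats a ceiling but not the floor, so a reader may take the list as complete. Under the combined rule, the 6-month limit in the opening sentence never operates when H is above 0, so that sentence does not describe exactly who is enrolled. The protocol does not say that this narrowing was intended. All the passages are current text, so the mismatch is not left over from an amendment.

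The textual points stand: two dates are used, and the minimum appears in only one part of the eligibility section. The consequences are weaker. Early enrolment requires setting aside a plain statement of whom the study will include, printed at the head of the same section and echoed by the 3-month minimum in hypothesis 2. Patients come from the ICUs of one hospital, and the Study 2 procedures refer to a single study site, so many sites reading the list differently is not a realistic worry. The argument about weaker patients needs two things the protocol does not supply: that the longer hospitalization falls after the ICU, and that a shorter eligible period means patients are actually missed. Reporting time since both discharges would help readers, but leaving it out of the protocol is not a fault in the design.

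**Conclusion.** The concern does not call for a change. The wording is uneven, but the rules are compatible, and applied together they enrol only patients within the 3 to 6 months after ICU that hypothesis 2 names. The floor missing from the numbered list is stated a few lines above it, so adding it there would only repeat a rule. Moving to a single anchor date is a trade-off, since either choice lets in patients whom the combined rule keeps out.

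The only real effect is that the eligible period is shorter by H. If H is between 0.25 and 0.5 month, 2.5 to 2.75 of the 3 months remain; at 2 months only 1 remains. The documents do not show where H lies, so the number of patients affected is unknown. The Study 2 target of 20 patients and 20 controls rests on no formal calculation, and no power or significance figure depends on these dates.

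The conclusion assumes that the opening sentence is read as an eligibility rule and applied together with the numbered criteria, which is the ordinary reading.

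### Study 1 prints one fixed block size of four while the physiotherapist role both opens envelopes and helps judge suitability, so the next allocation is partly predictable at enrolment

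*Protocol*

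**What the plan says.** Under Statistical considerations, Randomization, the protocol fixes one block size for Study 1: "randomization will be determined using a computer-generated sequence in permuted blocks of four". On concealment it says "Treatment allocation is concealed in opaque envelopes prepared by a research associate not involved in the study", and then "The envelope is opened by the physiotherapist supervising the exercise session just before the intervention". Outcome assessors are blinded until the data analysis is complete.

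Study 1 inclusion criterion 2 reads "Suitable for active mobilization as determined by the attending physician and physiotherapist". The Study populations section places recruitment in a single unit and says of active mobilization "which is already standard care in the unit at Karolinska University Hospital Huddinge".

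The Sample size section says "10 patients in each treatment arm are required" and then "To account for potential dropouts we will enroll a total of 24 patients". The primary outcome is a comparison of changes: "The primary outcome is the difference in change between the intervention and control groups in lower limb protein balance, from baseline to post-intervention".

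The protocol does not say how many physiotherapists take part, or whether the one who judges suitability also opens envelopes.

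**The concern.** The treatment cannot be hidden from the physiotherapist who supervises it, so that role accumulates knowledge of past allocations. The same role helps decide who enters. The safeguards act elsewhere: the envelopes and their late opening protect the current patient's assignment, and blinded assessors protect the measurement. Neither prevents inference from past allocations to the next one, and a small fixed block makes that inference easier.

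What is at stake is selection bias at enrolment. Because the outcome is change from baseline, stable differences in level between patients cancel. Steering would matter only if the steered patients differ in the change itself, for example if patients judged fitter respond more to exercise. If they do, blinded assessment would not remove the effect, and each arm has only 10 to 12 patients.

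**Working it through.** **Inputs.** Block size 4 (Randomization). 24 enrolled, so 24/4 = 6 blocks (Sample size). A 1:1 ratio within blocks is inferred from the equal arm targets; no ratio is printed. The protocol gives no figure for predictability, and no effect size or SD, so there is nothing of its own to reproduce here.

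**1. Certain allocations (block size, boundaries and all earlier allocations known).** An allocation is certain once one arm's two places in the block are used. The orders AABB, ABAB, ABBA, BAAB, BABA and BBAA leave 2, 1, 1, 1, 1 and 2 certain. The mean is 8/6 = 4/3 per block, and 6 × 4/3 = 8.0 of 24. The count is 6 + Binomial(6, 1/3): range 6 to 12, with probability 0.32 of more than 8.

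**2. Best guess, same knowledge.** Guess the arm that is behind. Chances of being right at places 1 to 4 are 1/2, 2/3, 1/3 × 1 + 2/3 × 1/2 = 2/3, and 1. The sum is 2.833; 6 × 2.833 = 17.0, and 17.0/24 = 71%, against 50% by chance.

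**3. Steering model (assumed).** A patient changes by v more when exercise is guessed, v less when control is guessed, and 0 at a tie. The expected shift in the arm difference is (correct − wrong)v/12. At full knowledge this is (17 − 7)v/12 = 0.83v. Since correct + wrong = 24 (ties counted half each), correct = 12 + 6 × shift/v.

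**4. Partial knowledge, blocks of four.**

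| Earlier allocations known | Certain (boundaries known) | Best guess right (boundaries known) | Shift (boundaries unknown) | Best guess right (boundaries unknown) |
|---|---|---|---|---|
| 100% | 8.0 | 71% | 0.83v | 71% |
| 75% | 4.5 | 65% | 0.39v | 60% |
| 50% | 2.0 | 60% | 0.24v | 56% |
| 25% | 0.5 | 55% | 0.14v | 53% |

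The last column follows from step 3; for example 12 + 6 × 0.241 = 13.45, and 13.45/24 = 56%.

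**5. False-positive rate.** Simulated, 12 per arm, two-sided 5% t-test of change on 22 df, used as a simple stand-in for the planned repeated measures ANOVA. The values of v are assumed.

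| v | Full knowledge | 50% known, boundaries unknown |
|---|---|---|
| 0.1 SD | 5.4% | 5.0% |
| 0.25 SD | 7.2% | 5.3% |
| 0.5 SD | 14.5% | 5.5% |

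**6. Alternatives, all earlier allocations known.** For one block of size m, expected correct guesses are m/2 + (2^m/C(m, m/2) − 1)/2; m = 4 gives 2.833, as in step 2.

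- Blocks 6, 8 and 10, each once: 4.10 + 5.33 + 6.53 = 15.96, or 66%; shift (2 × 15.96 − 24)v/12 = 0.66v. Sizes drawn at random instead give about 0.63v. About 2 or fewer allocations are certain while the order of sizes is undisclosed. If the order were known, certain allocations would be m/(m/2 + 1) per block: 1.5 + 1.6 + 1.67 = 4.8.
- One 12:12 list: 14.60 correct, or 61%; shift (14.60 − 9.40)v/12 = 0.43v; 24/13 = 1.8 certain.

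At 50% knowledge without boundaries, even the single list lowers the shift only from 0.24v to 0.18v, about a quarter.

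**The case against.** Permuted blocks of four are conventional, and nothing in the protocol contradicts anything else. Concealment is well arranged for the current patient: an uninvolved associate prepares opaque envelopes, which are opened only after catheterization and baseline sampling. Suitability is decided jointly with the attending physician and concerns active mobilization, which both arms receive. Entry also requires an arterial line, no expected discharge or transfer within 24 hours, consent and the other exclusion criteria. The steering route is therefore narrow, whereas the model steers every patient whenever the known counts differ. The size of v comes from nothing in the protocol and may be zero.

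All of that stands. It limits the point to a possible improvement but does not remove it, because none of these safeguards breaks the link from past allocations to the next suitability judgement.

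A reader might infer that one physiotherapist knows a third of the assignments in advance, or that the test runs at about 14.5% instead of 5%. The documents support neither. They show a shared role, not a shared person. The 14.5% needs complete knowledge, steering at every opportunity and a 0.5 SD steering effect all together.

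**Conclusion.** The point holds as a minor weakness of design. A printed fixed block of four, combined with a role that both learns allocations and shares the entry decision, makes the next allocation partly predictable. The ceiling is 8 of 24 certain and 71% guessed correctly. In the less extreme case of half the earlier allocations known and boundaries unknown, it is about 56%, with a false-positive rate close to nominal in the assumed model.

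The figures rest on 1:1 blocks, a full 24 patients and, for shifts and error rates, assumed values of v. The documents do not show that steering occurred or that Study 1 is biased, and they leave open whether one person fills both roles.

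**What to change.** For allocations not yet made, starting at the end of the current block, use randomly varied larger blocks. For a full 24, sizes 6, 8 and 10 in random order still end 12:12. The research associate who prepares the envelopes should alone hold the scheme, and the protocol should not print the sizes. Merely hiding the size while keeping blocks of four would leave the 71% unchanged.

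With all earlier allocations known, this lowers certain allocations from 8 to about 2 or fewer, correct guesses from 71% to about 66%, and the shift from 0.83v to about 0.63v to 0.66v. At partial knowledge the gain is small.

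The cost is a new list and envelopes, plus a small imbalance if recruitment stops within a block. Stopped at 20, blocks of four give 10:10. With 6, 8 and 10 the last block is short by four, and those four split 2:2 with probability 9/15, 36/70 or 100/210 according to its size, on average 0.53. One arm would then be below 10 with probability about 47%, usually at 11:9; 12:8 has probability (0 + 2/70 + 10/210)/3 = 2.5%.

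A single 12:12 list lowers predictability further but is an optional trade-off. Stopped at 20, it leaves one arm below the required 10 with probability 1 − C(12,10)²/C(24,20) = 1 − 4356/10626 = 59%, and gives 12:8 with probability 9%. A 12:8 split costs 1 to 2 points of power under assumed effects of 0.8 to 1.32 SD. Stopped at 12, the single list gives 8:4 or worse with probability 22%, against 2/6 × 10/210 = 1.6% for the varied blocks.

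If Study 1 allocation is already complete, the change no longer applies.
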